4.5 Selection and Timing of Dose for Each Subject

Subjects will be administered study medication as a continuous IV infusion over 48 hours.

Body weight measured at screening will be used for dose calculations.

Every effort must be made to initiate study drug administration promptly after randomization.

See Pharmacy Manual for additional dosing information.

4.5.1 Dose Reductions, Temporary Interruptions, and Permanent Discontinuations of Study Drug Due to Blood Pressure

Any decision to lower the dosage level of study drug or discontinue study drug should be based on the Investigators assessment of the subject's overall clinical stability, in the context of appropriate ongoing monitoring of the subject's condition. A 50% dosage adjustment downward maybe be achieved by decreasing the rate of study drug infusion.

In Part I (Cohort 1) subjects who require a dose reduction or temporary interruption during the first infusion period, hours 0 to 4 (dose of 3 µg/kg/min), will be permanently discontinued from study drug.

Study drug infusion rate may be reduced by 50%, temporarily interrupted, or permanently discontinued. See [Figure 4.5.1-1](#) and the following sections for more detail.

Dose Reduction:

- If the subject experiences SBP < 95 mm Hg, without symptoms related to hypotension, the measurement must be repeated within 15 minutes. If the SBP remains < 95 mm Hg, the dose reduction must occur
- A 50% dosage adjustment downward may be achieved by decreasing the rate of study drug infusion by half
- After a dose reduction, the dose cannot be increased again

Temporary interruption:

- If the systolic blood pressure reduces below < 85 mm Hg, and remains < 85 mm Hg during a repeated measure within 15 minutes, the study drug must be interrupted for at least 1 hour
- For subjects that report symptoms consistent with hypotension (eg, dizziness, lightheadedness, etc.), and are related to hypotension, study drug must be interrupted for at least 1 hour

[figure not shown]
Resuming Study Drug

- Study drug may be resumed at 50% of the dose after 1 hour interruption, if SBP rises to values ≥ 105 mm Hg and any symptoms of hypotension, if present, have resolved.
- If after 4 hours, the subject’s SBP remains below < 105 mm Hg, or if symptoms persist, then study drug must be permanently discontinued
- After a dose reduction, the dose cannot be increased again

Permanent discontinuation of the infusion:

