Central Laboratory Assessments			See Section 5.3.5.2 for Analytes
Hematology and Serum Chemistry		X	
Hs Troponin T		X	
NT-proBNP, Serum Cystatin C, NGAL		X	
CRP		X	
Urinalysis		X	
Urine creatinine, Na+, and K+		X	
Efficacy Assessments			
Resting Dyspnea measured by the Numerical Rating Scale (NRS) ^a		X	
Other Assessments			
Sensory Motor Survey		X	

^a If subject is receiving supplemental oxygen, perform NRS without removing oxygen

Table 5.1-2: Treatment and In-Hospital Follow-up (CV013011)

Procedure	Hour 0-23 ^a (Post Rand, Day 1)	Hour 24 ± 2	Hour 48 ± 2	Hour 72 ± 2	Hour 96 ± 2	Hour 120 ± 2 or Discharge ^{b c}	Notes (Time is relative to start of dosing)
Randomize Subject	X						Randomization must take place before Hour 0
Administer Study Medication		X					48 hour continuous infusion *Study medication infusion begin promptly after randomization*
Safety Assessments							
Body Weight		X	X	X	X	X	
Vital Signs: Blood Pressure and Heart Rate ^d	X	X	X	X	X	X	Perform Semi-Recumbent (at a 30° angle) Day 1: Hours 0, 0.25 (15 min), 0.5 (30 min), 0.75 (45 min), 1, 1.5, 2, 4, 5* , 6, 8, 9* , 10, 12, 14, 16, 18, 20, 22 Hours: 24, 28, 32, 36, 40, 44 Hours 48, 54, 60, 66 Hour 72 Hour 96 Hour 120 Perform measurements before IV bag change, when possible. Repeats as per Section 5.3.1 Perform also if signs or symptoms of hypotension *Part I (Cohort 1) only
Respiratory Rate	X	X	X	X	X	X	Day 1: Hours 6 and 12
Use of Oxygen Supplementation,	X	X	X	X	X	X	Day 1: Hours 6 and 12

Table 5.1-2: Treatment and In-Hospital Follow-up (CV013011)

Procedure	Hour 0-23 ^a (Post Rand, Day 1)	Hour 24 ± 2	Hour 48 ± 2	Hour 72 ± 2	Hour 96 ± 2	Hour 120 ± 2 or Discharge ^{b c}	Notes (Time is relative to start of dosing)
Oxygen Saturation							
Temperature		X	X	X	X	X	
12-Lead ECG		X	X	X		X	
Telemetry Monitoring	X						Continuous monitoring through Hour 50

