5.3.1 Assessment of Blood Pressure and Symptoms for Hypotension

The primary endpoint of the study is the incidence of clinically relevant hypotension, defined by SBP < 90 mm Hg (confirmed by a repeated value < 90 mm Hg) or symptoms of hypotension, up to 6 hours after the end of study drug infusion. Thus hypotension will be assessed by collection of symptoms and blood pressure measurements.

Symptomatic hypotension is defined as the presence of both low SBP and significant and/or non-resolving symptoms due to low blood pressure (eg, lightheadedness, dizziness, etc.).

Blood pressure measurements should be performed with the subject in a semi-recumbent (about a 30° angle) position, whenever possible.

Blood pressure will be measured as indicated in Table 5.1-2, within (\pm 5 min in the first hour then \pm 0.25 (15 min)) of the specified time points. In addition, sites may perform measurements at intervals defined by institutional standard of care for subjects receiving vasodilators, but no less than what is described in Table 5.1-2.

If the study drug dose is modified (decreased, interrupted, resumed or discontinued) the frequency of blood pressure measurements will follow a more intensive schedule for up to 6 hours following the dose modification (Table 5.3.1-1). Upon completion of the intensive schedule, measurements can be either resumed per the original schedule, or follow the discontinuation schedule if the drug is permanently discontinued.

Table 5.3.1-1: Schedule of Intensive Blood Pressure Collection Following a Dose Modification

	30 minutes post	1 hour post	2 hours Post	4 hours post	6 hours post
Dose reduction	X	X	X	X	X
Dose interruption ^a	X	X	X	X	
Dose resumption ^b	X	X	X	X	X
Dose discontinuation	X	X	X	X	X ^c

^a dose must be resumed within 4 hours of dose interruption. If interruption last beyond 4 hours, dose must be discontinued and discontinuation schedule must be followed.

^b If dose is restarted within 4 hours following interruption, follow schedule for dose resumption

^c After 6 hours, continue collecting blood pressure measurement at a minimum of every 12 hours through hour 72 or follow the local institutional standard of care protocol, whichever is more frequent.

In addition to assessments of blood pressure, the Investigator will be asked to collect and assess signs and symptoms of low blood pressure The details to be captured will include:

- Onset date/time
- Total duration of episode
- Lowest blood pressure during the episode

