8.3 Endpoints

8.3.1 Primary Endpoint

The primary endpoint is the incidence of clinically relevant hypotension, defined by SBP < 90 mm Hg (confirmed by a repeated value < 90 mm Hg) or symptoms of hypotension, up to 6 hours after the end of study drug infusion.

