8 CONVENTIONS

8.1 Safety Data Conventions

Except as noted in [Section 7.6](#), safety data will be handled according to the BMS safety data conventions. This document includes descriptions on how to analyze AE data as well as how to handle partial dates, missing dates, and unknown end dates when analyzing safety data. If onset time of AEs is missing or incomplete, the onset date of AEs will be used to determine if the AEs will be included in the AE summary tables as follows.

- Non-serious AEs will be included in summary tables if the onset date is on or after the start date of study treatment and not later than the date of Hour 120.
- Serious AEs will be included in summary tables if the onset date is on or after the start date of study treatment and not later than the date of Day 32.

Clinically relevant hypotension defined in the primary endpoint consists of two components which are further clarified as follow:

- The component of “SBP < 90 mm Hg (confirmed by a repeated value < 90 mm Hg)” will be identified by a SBP measurement < 90 mm Hg with confirmatory SBP measurement < 90 mm Hg within 30 minutes after the initial qualifying value. If a confirmatory SBP is missing, the initial SBP will be treated as confirmed if no SBP measurement \geq 90 mm Hg within 30 minutes exists. The assessment time of the initial SBP < 90 mm Hg will include time from start of infusion, up to and including 6 hours after end of infusion.

The confirmatory measurement should be within 15 minutes; however, a window of up to 30 minutes will be applied, to determine if a qualifying confirmatory value is obtained.

- The component of “symptoms of hypotension” will be identified by at least one symptom (other than “low blood pressure”) from the CRF page collecting signs and symptoms of low blood pressure with onset time from start of infusion, up to and including 6 hours after end of infusion

This clarification is also applied to the safety endpoints “The incidence of symptomatic hypotension up to 6 hours after the end of study drug infusion, as well as the incidence of SBP < 90 mm Hg (confirmed by a repeated value)”.

Subjects counted in the endpoint “Percentage of subjects with discontinuation due to symptomatic hypotension” are those who have “Hypotension” as the reason for discontinuation and have a symptom (other than “low blood pressure”) from the CRF page collecting signs and symptoms of low blood pressure with onset time on or before the time of dose discontinuation.

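### SAP 8.1 counts an unrepeated SBP below 90 mm Hg as a confirmed primary event, while the protocol gives no timed order to repeat a low reading for the endpoint once the infusion has stopped

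*SAP*

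**What the plan says.** **The endpoint.** Protocol 8.3.1, repeated in 5.3.1, has clinically relevant hypotension "defined by SBP < 90 mm Hg (confirmed by a repeated value < 90 mm Hg) or symptoms of hypotension", counted until 6 hours after the infusion ends.

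**The SAP rule.** SAP 8.1 accepts a second value below 90 within 30 minutes of the first: "The confirmatory measurement should be within 15 minutes; however, a window of up to 30 minutes will be applied". It then adds: "If a confirmatory SBP is missing, the initial SBP will be treated as confirmed if no SBP measurement" of 90 mm Hg or more exists within 30 minutes. The initial reading may fall anywhere from the start of infusion "up to and including 6 hours after end of infusion". The same convention serves the separate endpoint of confirmed SBP below 90. SAP 7.6.1 counts subjects with at least one event. The public SAP text describes no analysis restricted to readings that were actually repeated.

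**When sites repeat a reading.** Protocol 4.5.1, under dose reduction, says of an asymptomatic SBP below 95 that "the measurement must be repeated within 15 minutes". Under temporary interruption it uses a 15-minute repeat for SBP below 85. Both lead to an action on a running infusion. The vital-signs row of Table 5.1-2 says "Repeats as per Section 5.3.1". Section 5.3.1 holds the endpoint definition, the details to record for an episode, and reading times after a dose change, when "the frequency of blood pressure measurements will follow a more intensive schedule for up to 6 hours following the dose modification". It contains no instruction to repeat a low value and no time limit for doing so.

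**The concern.** The definition and the rule that implements it disagree. Under the protocol an unrepeated low reading is not an event. Under the SAP it is one, unless a value of 90 or more was recorded within 30 minutes; a normal value at 35 minutes would not undo it.

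This matters most where no repeat is ordered. Once the infusion is over, the triggers in 4.5.1 have nothing to act on, yet the endpoint window stays open for 6 hours. The default is not confined to that period, because a missed repeat during infusion is handled the same way. A reassuring recheck may also never reach the database: Protocol 5.3 leaves standard-of-care measurements in the medical record unless they support an adverse event report or the sponsor asks for them.

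At stake is the primary endpoint of both parts, which is also a named input to the Part II dose decision (Protocol 8.5, SAP 7.11). A rate labelled as confirmed would contain an unknown number of unconfirmed events, and no planned table would show how many.

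**Working it through.** **1. The plan's own figures.** Inputs are from Protocol 8.1. With placebo and active counts x0 and x1 as independent binomials,

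P(flag) = Σ Bin(x0; n, p0) · Bin(x1; n, p1) over all pairs with x1 > k·x0 and (x1 − x0)/n > d.

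Part I: n = 50, k = 2, d = 0.04. Part II: n = 70, k = 1.8, d = 0.03.

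| Comparison | Plan | Computed |
|---|---|---|
| Part I, 5% v 20% | 86% | 85.9% |
| Part I, 10% v 30% | 80% | 80.3% |
| Part I, no increase (5%, 10% base) | 11–12% | 11.4%, 11.5% |
| Part II, 5% v 15% | 82% | 81.7% |
| Part II, 10% v 25% | 80% | 79.7% |
| Part II, no increase (5%, 10% base) | 13–15% | 15.2%, 12.7% |

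The figures reproduce, so the same formula is used below.

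**2. Off-drug readings with a partner within 30 minutes.**
- After discontinuation (Table 5.3.1-1), readings fall at 0.5, 1, 2, 4 and 6 h. The gaps are 0.5, 1, 2 and 2 h, so only the 0.5 h reading has a scheduled successor within 30 minutes. Four readings (1, 2, 4 and 6 h) have none.
- After a completed infusion (Table 5.1-2), Hour 54 is the only scheduled reading after Hour 48 inside the window, and the next is Hour 60. One reading has no partner.

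For these, a low value counts alone unless the site takes and records another.

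**3. Effect if single-reading events occur equally in both arms.** The documents give no rate, so assume a share e of otherwise event-free subjects: p becomes p + (1 − p)e. With e = 2%, 5% becomes 0.05 + 0.95 × 0.02 = 6.9%, 15% becomes 0.15 + 0.85 × 0.02 = 16.7%, and the risk ratio falls from 3.0 to 2.42. Detection probabilities:

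| e, both arms | Part I, 5% v 20% | Part II, 5% v 15% | Part II, 10% v 25% |
|---|---|---|---|
| 0 | 85.9% | 81.7% | 79.7% |
| 1% | 81.7% | 77.2% | 76.1% |
| 2% | 77.4% | 72.7% | 72.4% |
| 5% | 64.2% | 59.0% | 61.3% |

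**4. Effect if early stopping differs.** Assume each partnerless off-drug reading is low with probability q and a share D stops early: e = (1 − D)q + D[1 − (1 − q)^4]. For q = 1%, D = 10% on placebo gives 0.9 × 0.01 + 0.1 × 0.0394 = 1.29%; D = 30% on active gives 0.7 × 0.01 + 0.3 × 0.0394 = 1.88%. With no true increase, Part II false detection is then:

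| D, placebo / active | 5% base (15.2% without the rule) | 10% base (12.7% without the rule) |
|---|---|---|
| 10% / 30%, q = 0.5–2% | 17.6–20.8% | 13.0–13.6% |
| 5% / 5%, q = 0.5–2% | 15.5–15.9% | 10.8–12.2% |

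At the 10% base the result lies above or below 12.7% depending on D, which is assumed. The scenario also treats early stoppers as no more likely than others to have had an event already, and it ignores their shorter observation.

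**5. Conditional illustration for one subject.** Assume true SBP 98 throughout, independent normal error with SD 7, and no repeats ever taken. P(one reading < 90) = Φ(−8/7) = 0.127; P(reading and repeat both < 90) = 0.127² = 0.016. Over four readings, at least one counted event: 1 − 0.873^4 = 42% on single readings, 1 − 0.984^4 = 6% with a true repeat. SD 5 to 9 gives 20–56% against 1–13%. This shows only that one reading and two are different standards near the threshold.

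**The case against.** The best defence is that counting a missing repeat as an event is a pre-specified convention, the same in every arm and conservative for a safety endpoint. It resembles the worst-score handling of the dyspnea scales. Letting a missing repeat mean no event could hide real hypotension. This stands, and it is why the rule should be kept and supplemented.

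Sites are also not without a hint. The pointer in Table 5.1-2 covers Hours 48 to 66, 5.3.1 opens with the endpoint and its repeated value and asks for the duration and lowest pressure of an episode, and the SAP's 15-minute expectation is not limited to a running infusion. This stands in part: none of it tells a site to take a second reading by a given time, and the SAP does not instruct sites.

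Three stronger readings that a reader might infer are not supported:

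- **That off drug this becomes a one-reading endpoint.** One rule applies on and off drug. A recorded value of 90 or more within 30 minutes prevents the event, the 0.5 h and 1 h readings can pair, sites may measure more often, and the symptom route is unaffected.
- **That extra events fall mainly in the active arms**, since early stoppers have four partnerless off-drug readings and completers one. Each subject counts once, and those interrupted for confirmed SBP below 85 or for symptoms will normally have met the endpoint already. Early stopping also shortens observation. In Part II a subject stopped at Hour 8 has five scheduled readings up to Hour 14, whereas a completer has 15 after Hour 8 (10, 12, 14, 16, 18, 20, 22, 24, 28, 32, 36, 40, 44, 48, 54). Protocol 6.5 also reports recovery of pressure within 1–2 hours of stopping in earlier studies.
- **That three extra events would trip the sample decision rules.** They pass the difference part (3/50 = 6.0%, 3/70 = 4.3%), but the rules have a fold part too. 5/50 v 8/50 is 1.6-fold, 7/70 v 10/70 is 1.43-fold and 4/70 v 7/70 is 1.75-fold, and all three fail; 3/70 v 6/70 is 2-fold and passes. The rules are only examples, dose selection weighs all the data, and no significance test is planned.

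**Conclusion.** The point holds as a mismatch between the endpoint and its implementation. The SAP applies a looser SBP criterion than the protocol defines. Off drug, four of the five scheduled readings after discontinuation, and the only one after completion, can become primary events on a single value. Missed repeats during infusion fall under the same default, and no planned output separates the two kinds of event.

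The size is unknown, because the documents give no rate of unrepeated low readings. If single-reading events reached 1–2% of otherwise event-free subjects in both arms, detection in the three tabulated comparisons would fall by about 4 to 9 percentage points. The direction of any between-arm bias cannot be derived, since prior events and shorter observation in early stoppers work against their larger number of partnerless readings. This is a cheap improvement and does not invalidate the design.

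**What to change.** 1. **Protocol 5.3.1**, where Table 5.1-2 already points: state that, for endpoint ascertainment, any SBP below 90 from the start of infusion to 6 h after its end is repeated within 15 minutes and recorded in the CRF, whether or not drug is running. No dosing rule changes.
2. **SAP 8.1 and 7.6.1**: keep the missing-repeat rule as the conservative analysis. Add a pre-specified analysis of the primary endpoint, and of the separate confirmed SBP endpoint, in which the SBP component requires an actual second value below 90. Tabulate single-reading events by arm and by on- or off-infusion.

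The cost is one extra cuff reading per low value in an inpatient, one protocol sentence, some SAP wording and one extra table.
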